**6.12.5.3 % of patients with PTA > 35 dB and > 90 dB on Day 7, Day 14 and end of study visit (visit D84± 3)**

The proportion of patients with PTA >35 dB and >90 dB on pure tone audiometric air conduction testing at the given timepoints (Day 7, 14, and 84) will be summarized by treatment group alongside an exact confidence interval. The PTA that will be utilized here is the average of the hearing threshold of 3 contiguous most affected hearing frequencies in decibels as identified at study entry.

**6.12.5.4 % of responders (response is defined as an improvement of 10dB or more) in PTA**

For this endpoint, a subject will be classified as “responder”, that is, if the subject has an improvement of 10dB or more in PTA (pure tone audiometric air conduction testing) from baseline, or “non-responder” otherwise for each timepoint (Day 7, 14, 28, and 84). The PTA that will be utilized here is the average of the hearing threshold of 3 contiguous most affected hearing frequencies in decibels as identified at study entry. The % of responders will be summarized by treatment group at each timepoint alongside an exact confidence interval. In addition, the proportion of responders at each timepoint for each treatment arm will also be graphically represented.

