**The hearing threshold** is defined as the lowest audible level, measured twice out of three presentations for that patient. The thresholds at each frequency for each ear for both air and bone pure tone audiometry will be recorded on the e-CRF at each study visit. The information will be captured in case of no response because of profound hearing loss.

The **hearing loss** will be determined as follows: Difference between the mean hearing threshold at the 3 most affected contiguous test frequencies (air pure tone average) and the corresponding mean hearing threshold of the contralateral ear or values from a pre-existing audiogram (dated less than 2 years) for the same frequencies (mandatory for bilateral acute acoustic trauma).

The Pure tone average frequencies determined at baseline will remain fixed for all evaluations. In case of bilateral acute acoustic trauma leading to sudden sensorineural hearing loss, the most affected ear according to the inclusion criteria will be considered for the analysis. If both ears are equally affected, the right ear will be considered.

In case of one missing frequency in any of the post baseline measurement, the PTA will be determined on the 2 out of the 3 available frequencies. An absolute improvement of 10dB is considered clinically meaningful.

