### 3.2 Secondary Endpoints

- Change in pure tone audiometry (average of the hearing threshold of the 2 most affected hearing frequencies identified at study entry) in affected ear from baseline to the end of treatment visit (Visit D28± 3)
- Change in pure tone audiometry (the most affected hearing frequency identified at study entry) in affected ear from baseline to the end of treatment visit (Visit D28± 3)
- Change in pure tone audiometry (PTA; average of the hearing threshold of 3 contiguous most affected hearing frequencies in decibels as identified at study entry on pure tone audiometric air conduction testing) in affected ear from baseline to the end of study visit (Visit D84 ± 3)
- Change in speech discrimination threshold from baseline to Days 28, and 84
- Frequency and severity of tinnitus at Days 7, 14, 28, and 84 assessed by numerical rating scale

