## 6.12 Efficacy Analyses

For Part 1 all statistical tests will be performed using a one-tailed 5% significance level. All comparisons between treatments, where high dose vs. placebo will be tested first, and then testing conditionally low dose vs. placebo, will be reported with 90% confidence intervals for the difference.

For Part 2, all statistical tests will be performed using a two-tailed 5% significance level. All comparisons between treatments will be reported with 95% confidence intervals for the difference.

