**6.12.4.5 Frequency and severity of tinnitus at Days 7, 14, 28, and 84 assessed by numerical rating scale**

Mean changes from baseline of the severity of tinnitus (assessed numerical rating scale) at Days 7, 14, 28 and 84 will be analyzed using the same modeling approach as for the primary endpoint. For Days 7 and 14 the patients diary log data (PM measurements) will be used.

For each relevant timepoint the number and percentage of patients experiencing tinnitus will be tabulated. Severity of reported tinnitus will be summarized as counts and percentages as well on a scale from 0 (no tinnitus) to 10 (extreme tinnitus).

All data on reported tinnitus occurrences and severity will also be listed.

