**6.12.5 Exploratory Endpoints**

All the following endpoints will only be analyzed based on the ITT population. The results will be presented descriptively (with confidence intervals where indicated, 90% confidence intervals for Part 1 data, 95% confidence intervals for Part 2 data).

**6.12.5.1 % of patients with complete hearing recovery defined as PTA <20 dB or hearing similar to the unaffected contralateral ear**

The proportion of patients with a complete hearing recovery or hearing similar to the unaffected ear will be summarized at Day 28 and Day 84 alongside an exact confidence interval. Hearing in the affected ear will be considered similar to the unaffected one if the absolute difference in pure tone audiometric air conduction testing (average of the hearing threshold of 3 contiguous most affected hearing frequencies in decibels as identified at study entry) is < 5dB, and this rule will also be applied to cases where either an old audiogram was used or normative values were considered as reference (e.g. pre-existing contralateral hearing loss with no audiogram in the past 2 years). Patients with complete hearing recovery are those that have pure tone audiometric air conduction testing (average of the hearing threshold of 3 contiguous most affected hearing frequencies in decibels as identified at study entry) of < 20dB.

	Sponsor:	Sensorion
	Protocol Number:	SENS 401-201
STATISTICAL ANALYSIS PLAN. PHASE 2-3-4		

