**6.12.5.2 % of patients with marked improvement defined as PTA threshold absolute improvement > 30 dB**

The proportion of patients with marked improvement in pure tone audiometric air conduction testing (average of the hearing threshold of 3 contiguous most affected hearing frequencies in decibels as identified at study entry), that is, PTA at post-baseline minus baseline PTA is > 30dB, will be summarized by treatment group for Day 28 and Day 84 along with an exact confidence interval.

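### Tinnitus frequency, part of a secondary endpoint, and the exploratory binary hearing endpoints have no pre-specified difference from placebo; adding one for a few rows is a cheap improvement

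*SAP*

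**What the plan says.** **Tinnitus.** SAP 3.2 lists as a secondary endpoint "Frequency and severity of tinnitus at Days 7, 14, 28, and 84 assessed by numerical rating scale". SAP 6.12.4.5 treats the two halves differently. Severity goes through the same repeated-measures model as the primary endpoint. For frequency, "For each relevant timepoint the number and percentage of patients experiencing tinnitus will be tabulated". In SAP 6.12.6, the title of item 6 carries both words, but its sub-items a to d are severity at Days 28, 14, 7 and 84.

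**Binary hearing endpoints.** These are exploratory. SAP 6.12.5 opens by saying "The results will be presented descriptively (with confidence intervals where indicated", at 90% in Part 1 and 95% in Part 2. The individual entries are:

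- Complete recovery (6.12.5.1): "will be summarized at Day 28 and Day 84 alongside an exact confidence interval".
- Marked improvement (6.12.5.2): "will be summarized by treatment group for Day 28 and Day 84 along with an exact confidence interval".
- 10 dB response (6.12.5.4): "The % of responders will be summarized by treatment group at each timepoint alongside an exact confidence interval".

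The proportions above 35 and 90 dB (6.12.5.3) follow the same pattern. SAP 6.3 lays out efficacy tables in treatment-group columns.

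**Related text.** Protocol 10.1.1 states: "An absolute improvement of 10dB is considered clinically meaningful". For Part 2, SAP 6.12 says: "All comparisons between treatments will be reported with 95% confidence intervals for the difference". For Part 1 it sets 90% intervals.

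**The concern.** A responder rate within one arm mixes natural recovery and the effect of background oral corticosteroids with any effect of SENS-401. Protocol 5.1 puts spontaneous recovery at up to 32% to 65% of cases and adds that this may be too high. Only the contrast with placebo isolates the drug. The plan gives each arm its own interval and leaves the reader to judge the contrast by eye.

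Two things are at stake. First, if the difference is wanted later, SAP section 6 allows documented extra analyses in the study report, but their method and visit would then be chosen with the data in view. Second, a reader of item 6 cannot tell from its title whether tinnitus frequency was meant to be tested.

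**Working it through.** **1. What is planned, endpoint by endpoint.**

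| Endpoint | Status | Planned statistic | Estimate against placebo |
|---|---|---|---|
| Tinnitus severity | Secondary, item 6a to 6d | Repeated-measures model | Yes |
| Tinnitus frequency | Secondary, named in item 6 | Count and percentage | None specified |
| Complete recovery | Exploratory | Proportion, exact CI | None specified |
| Marked improvement | Exploratory | Proportion, exact CI | None specified |
| 10 dB response | Exploratory | Proportion, exact CI | None specified |

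**2. Arm sizes, checked because the illustration uses them.** n per arm = 2(z_alpha + z_power)² SD² / difference².

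- Part 1: one-sided 5%, 75% power, 15 dB, SD 30 × √(1 − 0.45²) = 26.79. This gives 2 × (1.645 + 0.674)² × 26.79² / 15² = 34.3, so 35, which the plan raises to 37 for the group sequential design.
- Part 2: two-sided 5%, 90% power, 10 dB, SD 20. This gives 2 × (1.960 + 1.282)² × 20² / 10² = 84.1, so 85; then 85 / 0.90 = 94.4, so 95.

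Both match the plan. No binary endpoint has a stated size or power.

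**3. Illustration.** The documents give no expected responder rates. The counts below are assumed, with a placebo rate near 50%, inside the 32% to 65% range used as a stand-in. Per-arm intervals are Clopper-Pearson, as planned. The difference uses the Newcombe interval, built from the Wilson limits (l, u) of each arm:

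lower = d − √[(p1 − l1)² + (u2 − p2)²], upper = d + √[(u1 − p1)² + (p2 − l2)²].

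Part 1, 26/37 and 18/37: d = 0.703 − 0.486 = 0.216. The 90% Wilson limits are 0.569 to 0.809 and 0.357 to 0.618.

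- Lower = 0.216 − √(0.134² + 0.131²) = 0.029.
- Upper = 0.216 + √(0.106² + 0.130²) = 0.384.

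| | Exact CI, active | Exact CI, placebo | Difference (CI) |
|---|---|---|---|
| Part 1, 26/37 v 18/37, 90% | 55.6 to 82.3% | 34.3 to 63.2% | 21.6 points (2.9 to 38.4) |
| Part 2, 66/95 v 48/95, 95% | 59.2 to 78.5% | 40.1 to 60.9% | 18.9 points (5.0 to 31.9) |

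In both rows the per-arm intervals overlap although the interval for the difference excludes zero. For placebo counts nearest 32%, 50% and 65%, the difference interval excludes zero from about 19 points in Part 1 and 14 to 15 points in Part 2. The per-arm intervals separate only from about 27 to 30 and 19 to 21 points.

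**4. How much the added interval could show.** Approximate power over the same assumed placebo rates:

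- True 10-point difference: 22 to 24% in Part 1, 28 to 32% in Part 2.
- True 20-point difference: 54 to 64% in Part 1, 80 to 90% in Part 2.

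**5. How many intervals.** Covering every row would mean recovery 2, marked improvement 2, above 35 and 90 dB 6, 10 dB response 4 and tinnitus 4, which is 18. With two doses, Part 1 would have 36 intervals, and 36 × 0.05 = 1.8 favourable exclusions would be expected with no effect at all. Four Day 28 rows give 4 × 2 = 8 intervals, and 8 × 0.05 = 0.4.

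**6. Stratification.** The three binary factors form 2 × 2 × 2 = 8 cells. A dose and placebo together have 74 patients, so about 74 / 8 = 9 per cell on average.

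**7. Sign of marked improvement.** SAP 6.2.15 defines change as post-baseline minus baseline, and the alternative hypotheses in SAP 6.12.2 make a greater decrease the favourable direction. SAP 6.12.5.2 counts a patient when that change exceeds +30 dB. A move from 90 to 35 dB gives 35 − 90 = −55 and is not counted. A move from 35 to 90 dB gives +55 and is. As written, the endpoint counts worsening.

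**The case against.** Much of the case for leaving the plan alone stands. The hearing proportions are exploratory, Protocol 13.5.3 leaves their analysis to the SAP, and the SAP openly chooses description. No primary or ranked conclusion rests on them. For tinnitus, Protocol 13.5.2 plans a model for severity only, and since 0 on the scale means no tinnitus, absence already enters the modelled score.

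A reader might infer several stronger things that the documents do not support:

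- *That the arms are never compared, or that the trial cannot state an effect on these rates.* The arms are shown side by side, the crude difference and an interval follow from the counts, and the model compares mean PTA, from which the hearing proportions are derived. What is missing is a pre-specified estimate.
- *That SAP 6.12 is breached.* It governs how comparisons are reported once made; it does not require one for every endpoint.
- *That the protocol synopsis, which promises similar approaches for other efficacy endpoints, is contradicted.* That line is general; Protocol 13.5.3 is the specific provision for the exploratory endpoints.
- *That the plan loses power.* In Part 1, with assumed rates of 50% and 75%, separation of the per-arm intervals would occur 39% of the time, against 74% for a pooled two-proportion z-test. But the SAP nowhere says arms will be judged by overlap, so this measures a possible misreading and not a planned rule.

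What remains is that a mean change in PTA does not give the effect on the proportion reaching 10 dB or recovering, and that tinnitus frequency is not covered by the exploratory label.

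**Conclusion.** The point holds as an inexpensive improvement. It is strongest for tinnitus frequency, which is named in a secondary endpoint and in item 6 but has no planned estimate against placebo. It is weaker for the exploratory hearing proportions, where the gain is a directly readable effect size on a threshold that the protocol itself calls meaningful.

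The size can only be illustrated. The figures rest on assumed responder rates, borrowed from a range for spontaneous recovery rather than for a 10 dB gain on background steroids, and on a hypothetical overlap reading. They show that two exact intervals do not substitute for an interval on the difference. They do not show that any planned conclusion would be wrong. In Part 1 the added intervals will be wide. The reversed sign in SAP 6.12.5.2 follows from the SAP's own definitions and needs no assumption.

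**What to change.** - **Add the estimate.** Keep the per-arm exact intervals. In SAP 6.12.4.5, 6.12.5.1, 6.12.5.2 and 6.12.5.4, pre-specify the difference in proportions versus placebo, with 90% intervals in Part 1 and 95% in Part 2.
- **Limit it.** Day 28 only, four rows: tinnitus presence (score above 0), 10 dB response, complete recovery and marked improvement. Day 84 is optional.
- **Method.** Use a score-type or Newcombe interval, or a model-based marginal difference adjusted for baseline and the randomisation factors, instead of full stratification into 8 sparse cells. Tinnitus presence should be adjusted for baseline tinnitus, so it needs the model-based form.
- **Label.** State that these results are exploratory, unadjusted for multiplicity and outside the testing sequence.
- **Item 6.** Reword it to say that only severity is tested.
- **Sign first.** Before comparing arms on marked improvement, restate 6.12.5.2 so that a fall in PTA of more than 30 dB counts as improvement, in line with its heading.

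The cost is a few SAP sentences and extra columns in tables 14.2.2.5.3, 14.2.3.1, 14.2.3.2 and 14.2.3.4, with no new data. The downside is 8 unadjusted intervals in Part 1 and 4 in Part 2, or twice that if Day 84 is included.

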**6.12.5.5 Word recognition score at 80 dB and 60 dB in the affected ear on Day 28 and 84**

The word recognition score (that is, percent of words correctly repeated) at 80 and 60 dB in the affected ear and its changes from baseline to post-baseline timepoints will be summarized by treatment group using descriptive statistics for continuous variables. In addition, the following graphical displays will be presented:

	Sponsor:	Sensorion
	Protocol Number:	SENS 401-201
STATISTICAL ANALYSIS PLAN. PHASE 2-3-4		

- Percent change from baseline in Word Recognition Score in the affected ear by dB level over time, with a reference line at 15% to identify the clinically relevant improvement threshold.
- Word Recognition Score for the affected ear over time, by treatment group and dB level
- Difference in Word Recognition Scores between the affected and reference ear over time, by treatment group and dB level

All word recognition data on both ears will be listed.

***6.12.5.6 Relationship between time of onset of symptoms to first study drug intake and the primary endpoint***

The time of onset of symptoms to first study drug intake (in days) will be obtained as follows:

date of first dose of study drug – date of the onset of SSNHL symptoms and will be summarized descriptively by treatment group.

The relationship between time of onset of symptoms to first study drug intake and the change in PTA at Day 28 from baseline will be explored through a scatter plot along with the Pearson correlation coefficient.

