
performed 24 hours or less prior to first study treatment, compared with the unaffected contralateral ear or reference values from a pre-existing audiogram (dated less than 2 years)
 
 
4. Patients with sudden hearing loss with onset within 96 hours prior to first study drug intake.
 
5. Females must meet one of the following: postmenopausal defined as 12 consecutive months with no menses without an alternative medical cause, surgically sterile, abstinent; or practicing highly effective birth control (must agree to use 2 forms of contraception [1 of which must be a barrier method]) (Appendix 4) and willing to continue to use highly effective contraception for the duration of study participation and for 30 days after the final dose of study drug). Women of childbearing potential must have a negative pregnancy test at screening before the first dose of study drug is taken. Women of childbearing potential are defined as any female who has experienced menarche and who is not permanently sterile or postmenopausal.
 
6. Male subjects and their female partner(s) must agree to use highly effective contraception (must agree to use 2 forms of contraception [1 of which must be a barrier method]) (Appendix 4) for the duration of study participation and for 90 days after the final dose of study drug.
 
7. Signed and dated written informed consent.
 
		

Exclusion criteria
		

Patients who have met all the above inclusion criteria listed in Section 8.1 will be screened for the following exclusion criteria:
		

 
1. Bilateral idiopathic hearing loss
 
2. Fluctuating hearing loss
 
3. History of asymmetric hearing (>20dB difference between ears) to the best knowledge of the patient
 
4. Severe hearing loss (>90 dB) associated with unilateral (ipsilateral) complete vestibular loss
 
5. History of Ménière's disease, autoimmune hearing loss, radiation-induced hearing loss, acoustic neuroma (schwannoma)
 
6. Previous SSNHL in the affected ear within the past 6 weeks
 
7. History of otosclerosis, suspected perilymph fistula or membrane rupture, suspected retro-cochlear lesion, barotrauma
 
8. Congenital or hereditary hearing loss
 
9. History of severe head or neck trauma
 
10. Complete loss of peripheral vestibular function on the affected side
 
		

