## 9.6 Accountability and compliance

The date and time of the first intake will be recorded on the eCRF.

The patient will be instructed to return all used and unused investigational kits at every on-site visit. He/she will be provided a diary to record the intake of IP (number of tablets, date and time). The investigator or designee will count the returned tablets and complete the corresponding e-CRF.

The type and dose of corticosteroids will be recorded on the eCRF. The patient will record the intake of corticosteroid in the diary. Corticosteroids intake will be also recorded on the e-CRF, based on the patient's information.

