### 6.7.2 Disease Characteristics and Other Relevant Baseline Data

The following variables will be summarized:

- Duration of current hearing loss episode at time of randomisation (in hours): randomisation date/time-SSNHL onset date/time, continuous and by class (<24 hours, [24; 48[, [48; 72[, >72 hours)
- Cause of current hearing loss/SSNHL: idiopathic, trauma (including noise induced), infectious, otologic disease, ototoxic drug intake, vascular/hematologic, neoplastic
- Oral Corticosteroids (CM.CMCAT = “ORAL STEROID”) for SSNHL (CM.CMINDC = “SSNHL”) at baseline (ongoing or started the day of first study treatment intake): yes/no and type (prednisone/prednisolone, methylprednisolone, dexamethasone or other)
- Otologic history: ear used for telephone and recent switch, professional exposure to very loud noise, recreational exposure to very loud noise, history of severe ear problems (previous SSNHL, frequent otitis media, past history of ear surgery, wearing hearing aids, past history of tinnitus in each ear), ear/head/neck/nose/throat problems (infection, respiratory tract infection, ear pain, ear pressure, otorhea, severe headache or migraine, recent head or neck trauma, recent baro trauma, exposure to loud noise, past otologic evaluation)

	Sponsor:	Sensorion
	Protocol Number:	SENS 401-201
STATISTICAL ANALYSIS PLAN. PHASE 2-3-4		

- Baseline Pure Tone Audiometry air conduction average of the hearing threshold of 3 contiguous most affected hearing frequencies in decibels as identified at study entry (PTA) for the current hearing loss episode:
  - Initial frequency range ( $\leq 2000$  Hz,  $> 2000$  Hz) derived as the mean between the lowest and the highest of the most affected frequencies
  - Affected ear side (right, left)
  - Affected ear PTA continuous (in decibels)
  - Affected ear PTA by class ( $<20$  dB,  $\geq 20$  dB to  $\leq 35$  dB,  $>35$  dB to  $\leq 50$ dB,  $>50$  to  $\leq 70$  dB,  $>70$  to  $\leq 90$  dB,  $>90$  dB)
  - Reference type (contralateral ear, previous PTA, reference frequency)
  - Reference PTA continuous
  - Reference PTA by class
  - Hearing loss (difference between the PTA on affected ear and the reference PTA for the identified frequencies) continuous (in decibels)
  - Hearing loss by class according to American Speech-Language-Hearing Association criteria (ASHA) ( $<16$ , 16 to  $<26$ dB, 26 to  $<41$ dB, 41 to  $<56$ dB, 56 to  $<71$ dB, 71 to  $<91$ dB,  $\geq 91$ dB)

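### SAP 6.12.5.6 measures onset-to-first-dose time as a calendar-date difference (values 0 to 4) although clock times are recorded, which modestly attenuates the exploratory Pearson correlation

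*SAP*

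**What the plan says.** SAP 6.12.5.6 sets the unit in its opening line, "The time of onset of symptoms to first study drug intake (in days"), and the derivation as "date of first dose of study drug – date of the onset of SSNHL symptoms". No clock time enters. The variable is summarised by treatment group, and its relationship with the Day 28 change in PTA "will be explored through a scatter plot along with the Pearson correlation coefficient". SAP 6.12.5 states that the exploratory endpoints are presented descriptively.

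The possible range is set by eligibility (Protocol section 3, repeated in 8.1): "Patients with sudden hearing loss with onset within 96 hours prior to first study drug intake".

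Both clock times are used elsewhere. For the dose, Protocol 9.6 says "The date and time of the first intake will be recorded on the eCRF". For onset, SAP 6.7.2 lists "Duration of current hearing loss episode at time of randomisation (in hours): randomisation date/time-SSNHL onset date/time", reported continuously and in classes. Randomisation is stratified at 24 hours of hearing loss (Protocol 9.3, SAP 5), and Protocol 7.1 calculates disease duration from the reported time of onset. Protocol Appendix 5, by contrast, names only the date of onset among the source data.

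**The concern.** The SAP measures almost the same interval twice: in hours for the baseline table, and in whole calendar days for the one endpoint that is about that interval. SAP section 8 gives no reason for the coarser unit.

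A date difference is not a rounded duration. It counts midnights, so it can reverse the order of two patients. Onset at 23:00 with dosing at 09:00 is a 10-hour delay coded 1; onset at 01:00 with dosing at 16:00 the same day is a 15-hour delay coded 0. Nor does the value line up with the trial's own 24-hour stratum.

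The relationship has a stated rationale. Protocol 5.1 lists time from onset to treatment among the prognostic factors, and 5.3.2 describes the effect in rats as time dependent, present up to 96 hours after the insult. At stake is a scatter plot that collapses into at most five vertical stripes and an r pulled towards zero.

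**Working it through.** The plan states no figure for this correlation, so there is nothing to reproduce.

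**Inputs from the documents.** Interval at most 96 hours (Protocol 3 and 8.1); derivation is date minus date (SAP 6.12.5.6); Part 1 has 111 patients (SAP 4), used only for scale.

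**Assumed inputs.** The distribution of the true delay T and the clock hour of dosing. The documents give neither, so several choices are shown.

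**Step 1: possible values.** Let D be the dose date minus the onset date. T ≤ 96 h is at most four full days, so D is 0, 1, 2, 3 or 4.

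**Step 2: what a value covers.** If dosing falls at clock hour h, then D = 0 when T ≤ h, and D = 1 when h < T ≤ h + 24. With h between 9 and 18:
- D = 0 holds delays of up to 18 h.
- D = 1 holds delays from 9 h to 18 + 24 = 42 h.
- With T uniform on 0–24 h and h uniform on 9–18 (mean 13.5), the share of delays under 24 h coded 1 is (24 − 13.5)/24 = 0.4375, about 44%.

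**Step 3: attenuation.** If the PTA change is linear in true hours and the error in D is unrelated to it given T, the expected r is multiplied by corr(T, D). Simulation with 2 million uniform delays per scenario gives:

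| True delay (uniform) | Dosing 09:00–18:00 | Dosing at any hour |
|---|---|---|
| 0–96 h | 0.97 | 0.94 |
| 0–72 h | 0.95 | 0.90 |
| 24–72 h | 0.90 | 0.82 |
| 0–48 h | 0.90 | 0.82 |

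An exponential delay with mean 24 h, truncated at 96 h, gives 0.95 and 0.90.

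The any-hour column has a closed form. Given T, D is T/24 rounded up or down with the matching probability, so its mean is exactly T/24. If f is the fractional part of T/24, the variance is f(1 − f), which averages 1/6 day², or 576/6 = 96 h². Hence corr = √(Var T/(Var T + 96)):
- T uniform on 0–96 h: Var T = 96²/12 = 768, so √(768/864) = 0.94.
- T uniform on 0–48 h: Var T = 48²/12 = 192, so √(192/288) = 0.82.

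**Step 4: scale.** Shrinkage runs from 1 − 0.97 = 3% to 1 − 0.82 = 18%. A true |r| of 0.30, chosen for illustration, would appear as 0.30 × 0.97 = 0.29 down to 0.30 × 0.82 = 0.25. The standard error of r at n = 111 is about (1 − 0.30²)/√110 = 0.09. The shift of 0.01 to 0.05 is therefore about 0.1 to 0.6 of a standard error.

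**The case against.** The strongest case against is that the consequence is small. SAP 6.12.5 makes this output descriptive, with no alpha, power or decision attached, and the shift is well within sampling error. That stands. A reader might infer that statistical power is lost or that the efficacy conclusions are at risk. The documents do not support either: no test is planned on this correlation, and the primary model uses the 24-hour stratum as entered in the IWRS, not this variable.

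Second, hours are not an exact truth. Onset is patient-reported, Protocol 5.1 defines sudden hearing loss as developing over up to 72 hours, and Appendix 5 requires only the onset date as source data. This also stands in part: for any assumed distribution, the attenuation computed against exact hours is an upper estimate of what switching would recover. It does not show that onset time is unavailable, because 6.7.2 and the 24-hour stratum cannot be carried out without it.

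Third, hour-level duration is already tabulated at randomisation, and Protocol 11.1.2 has the first dose taken on site straight after baseline assessments. That is true, but it does not enter the 6.12.5.6 correlation.

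Two further readings go too far. One is that a 2-hour and a 22-hour delay would commonly share the value 0. With dosing by 18:00, day 0 holds at most 18 hours, so that pairing needs late-evening dosing; the 9-to-42-hour spread at value 1 is the sound illustration. The other is that 3% to 18% is a bound. It is a range over assumed distributions, and other distributions could fall outside it.

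**Conclusion.** The point holds as a free improvement of the lowest severity. The predictor in 6.12.5.6 is coarser than the data allow and inconsistent with 6.7.2. The expected effect is attenuation of an exploratory Pearson r by about 3% to 18%. This rests on assumed delay and dosing-time distributions, a linear relationship with hours, and onset times treated as exact. The primary analysis, the type I error and the Part 2 comparison are unaffected.

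**What to change.** In SAP 6.12.5.6, replace the derivation with first-dose date/time minus SSNHL onset date/time, in hours, and use it for the descriptive summary, the scatter plot and the Pearson coefficient.

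State a rule for a missing onset time, since SAP 6.2.7 covers only partial diagnosis dates. Leave these patients out of the hour-based correlation and report how many there are. Filling in with date differences would put two error scales into one variable.

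Adding the time of onset to the Protocol Appendix 5 source list would align it with what 6.7.2 and the stratification already need.

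The cost is one revised derivation, the missing-time rule, and relabelling of Table 14.2.3.6 and Figure 14.2.1.9 for each part. No new data collection is required. The one trade-off is that patients without an onset time drop out of this correlation.
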